## **1. INTRODUCTION**

This document describes the planned data summaries and statistical analyses for Part B of Protocol A1481316, entitled “A Multi-centre, Randomized, placebo-controlled, double-blind, two-armed, parallel group study to evaluate efficacy and safety of iv sildenafil in the treatment of neonates with persistent pulmonary hypertension of the newborn (PPHN) or hypoxic respiratory failure and at risk for PPHN, with a long term follow-up investigation of developmental progress 12 and 24 months after completion of study treatment”. It is meant to supplement the study protocol which should be referred to for details regarding the objectives and design of the study. Any deviation to this analysis plan will be described in the Clinical Study Report.

Note: in this document any text taken directly from the protocol is *italicised*.

### **1.1. Study Design**

*This study will be conducted in two parts. Part A is the double-blind phase to assess the efficacy and safety of IV sildenafil versus placebo when added to iNO for no more than 14 days, during the acute phase of the disease, with follow-up at 7 and 28 days after the end of study drug infusion. Part B is the long-term, non-interventional phase, during which all subjects will be encouraged to return at 12 and 24 months after the end of study drug infusion, to take part in developmental assessments, hearing and ophthalmology tests.*

*Analysis of the double-blind phase of the study (Part A) will be performed when all subjects have completed or discontinued from the double-blind phase, and a study report will be written. Analysis of the non-interventional phase of the study (Part B) will be performed when all subjects have completed or discontinued from the 2-year follow-up visit, and a final study report will be written.*

### **1.2. Study Objectives**

The objectives for Part B of the study are:

- *The secondary objectives of this study are to evaluate the developmental progress of patients with PPHN treated with IV sildenafil or placebo, 12 and 24 months after the end of study treatment.*

## **2. INTERIM ANALYSES, FINAL ANALYSES AND UNBLINDING**

There is no interim analysis planned for the study.

The study will be un-masked after the last subject completed the Part A of the study and the database for Part A of the study is locked.

### **3. HYPOTHESES AND DECISION RULES**

#### **3.1. Statistical Hypotheses**

There are no formal statistical hypotheses for Part B of the study.

#### **3.2. Statistical Decision Rules**

Not applicable.

### **4. ANALYSIS SETS**

All subjects enrolled in Part B of the study will be included for data analyses on developmental progress, audiological, neurological and ophthalmological assessment, and safety.

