### **5. ENDPOINTS**

#### ***Part B:***

***Long-term Assessments:*** Monitored at 12 and 24 months after completion of study treatment:

- *Developmental progress, audiological and visual acuity assessments;*
- *Safety, assessed by adverse events, and survival.*

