#### **5.2. Safety Endpoints**

Adverse events (AE), including serious adverse events (SAE) and death.

Survival rates at Month 12 and 24 after completion of study treatment.

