## **7. STATISTICAL METHODOLOGY AND STATISTICAL ANALYSES**

### **7.1. Statistical Methods**

For continuous variables, summary statistics of n, mean, standard deviation, median, minimum and maximum will be tabulated by treatment group (iNO+ sildenafil vs. iNO alone in Part A of the study).

For categorical variables, n (%) of subjects in each category will be tabulated by treatment group (iNO+ sildenafil vs. iNO alone) in Part A of the study.

For subjects with multiple records in a given visit, the one with assessment date closest to the target visit day (see [Appendix](#)) will be selected for tabulation; for two observations with equal distance from the target visit day, the one assessed at a later time will be selected for tabulation.

All observations will be included in data listings for the endpoints listed below.

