### **7.2. Statistical Analyses**

#### **7.2.1. Analysis of Safety Endpoints**

All adverse events will be coded and grouped by system organ class. The incidence of each adverse event will be tabulated by treatment group. Tabulations by maximum severity and treatment group will also be included.

Data listings will be provided for adverse events, serious adverse events and death.

The duration of overall survival will be summarized graphically using Kaplan-Meier plots for each treatment group. Tabular summaries of the Kaplan-Meier curves giving the median, quartiles, mean, standard error of the mean and range of overall survival will also be provided for each treatment group. Number of deaths and survival rate at Month 12 and 24 will be tabulated by treatment group.

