### **8. APPENDIX**

#### **Appendix 1. DEFINITION AND USE OF VISIT WINDOWS IN REPORTING**

Visit Label	Definition [Day window]
Month 12	Date of Assessment – Date of Last Day on Study Treatment in Part A of the Study: [1 to 540] with target day of 360
Month 24	Date of Assessment – Date of Last Day on Study Treatment in Part A of the Study: $\geq 541$ with target day of 720

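### Survival is analysed in subjects enrolled in Part B but timed from the end of Part A treatment, so if enrolment comes later, deaths in between are left out of the by-arm rates

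*SAP*

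**What the plan says.** Section 4 of the SAP gives one analysis set for Part B: "All subjects enrolled in Part B of the study will be included for data analyses on developmental progress". The sentence goes on to cover the hearing, neurological and eye assessments, and safety.

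Section 5 places survival under safety, "Safety, assessed by adverse events, and survival", and describes the long-term assessments as "Monitored at 12 and 24 months after completion of study treatment". Section 5.2 lists as a safety endpoint "Survival rates at Month 12 and 24 after completion of study treatment". Appendix 1 counts visit days from the "Date of Last Day on Study Treatment in Part A of the Study".

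Section 7.2.1 plans the analysis: "The duration of overall survival will be summarized graphically using Kaplan-Meier plots for each treatment group", and "Number of deaths and survival rate at Month 12 and 24 will be tabulated by treatment group". Under Section 7.1 the groups are the Part A arms; results are "tabulated by treatment group (iNO+ sildenafil vs. iNO alone in Part A of the study").

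Section 1.1 assigns the visits at 7 and 28 days after the infusion to Part A. It describes Part B as a non-interventional phase in which subjects are invited back at 12 and 24 months.

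**The concern.** The survival clock starts at the end of Part A treatment. The only set that governs survival is defined by membership of Part B. If membership begins later than the clock, the children in the set had to survive the interval between the two in order to be counted. Deaths in that interval, including any during the 28-day Part A follow-up, are then excluded by the definition of the set.

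The Month 12 and 24 rates would be labelled as survival since the end of treatment but would describe survival among children who reached Part B. Because the tables are by randomised arm, a difference between arms in deaths during the gap would be hidden. Section 7.2.1 does not prevent this: it gives no separate survival population, no origin for the Kaplan-Meier curves, no handling of delayed entry and no rule for bringing in deaths recorded in Part A. Section 2 has the Part A database locked on its own, so their inclusion cannot be taken for granted.

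**Working it through.** The SAP gives no sample size, death rate or survival figure, so there is no figure of the plan to reproduce. **Every rate below is an assumption.**

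**Step 1. Set and clock side by side**

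| Item | SAP section | Content |
|---|---|---|
| Set for safety | 4 | Subjects enrolled in Part B |
| Survival is safety | 5, 5.2 | Yes |
| Origin of Month 12 and 24 rates | 5, 5.2 | Completion of study treatment |
| Day 0 of visit windows | Appendix 1 | Last day on Part A treatment |
| Kaplan-Meier origin | 7.2.1 | Not stated |
| Moment of Part B enrolment | – | Not stated |

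**Step 2. Size of the bias in one arm**

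Let q be the share of children alive at the end of treatment who die before Part B entry, and S_B the Month 24 survival in enrollees. Suppose that survivors who do not enrol have the same late survival.

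- Reported survival = S_B
- Survival of all children alive at the end of treatment = (1 − q) × S_B
- Overstatement = S_B − (1 − q) × S_B = q × S_B

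With S_B = 97%:

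| q | Reported | All alive at end of treatment | Overstatement (points) |
|---|---|---|---|
| 0% | 97.00% | 97.00% | 0 |
| 2% | 97.00% | 95.06% | 1.94 |
| 5% | 97.00% | 92.15% | 4.85 |
| 10% | 97.00% | 87.30% | 9.70 |

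The choice of S_B matters little. At q = 5%, S_B = 90% gives 0.05 × 90 = 4.50 points and S_B = 99% gives 0.05 × 99 = 4.95 points.

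**Step 3. Effect on the arm contrast**

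Take 100 children per arm alive at the end of treatment, with 2 deaths before Part B entry in one arm and 10 in the other, and 2 later deaths in each.

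- All children: 96/100 − 88/100 = 8.0 points
- Part B set: 96/98 − 88/90 = 97.96% − 97.78% = 0.2 points

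**Step 4. Sign**

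Let a share c of survivors not enrol, with late mortality m. Survival of all is then (1 − q) × [(1 − c) × S_B + c × (1 − m)]. With c = 30%, m = 0 and S_B = 97%, the bracket is 0.7 × 0.97 + 0.3 = 0.979.

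- At q = 0 the bias is 97.0 − 97.9 = −0.9 points.
- It is zero at q = 1 − 0.97/0.979 = 0.92% and positive above that.

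Understatement is therefore possible, if non-enrolled survivors do better and few children die in the gap.

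**Step 5. What deaths on treatment contribute**

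These precede the stated origin and add no bias to a rate counted from it. Suppose 5% die before Part B entry, counted from the start of treatment, and a share d of all children die on treatment. Then q = (0.05 − d)/(1 − d). For d = 0, 2.5% and 5%, q is 5.00%, 2.56% and 0%, and the overstatement at S_B = 97% is 4.85, 2.49 and 0 points.

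**The case against.** The strongest reply is that the concern depends on a fact the SAP does not contain. Section 1 sends the reader to the protocol for design, and the moment of enrolment is commonly fixed there. Section 1.1 speaks of one study in two parts, invites all subjects back and describes no separate Part B entry step. If everyone belongs to Part B from the start, nothing is lost and only the Kaplan-Meier origin needs a line. This stands: the bias is conditional. It does not remove the point, because Section 4 is where this SAP fixes the population and its wording permits the exclusion.

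A reader might go further and infer that enrolment happens at the first return visit, so that children entering on or after target day 360 would give a Month 12 survival of 100% by construction. The documents do not support that. No such entry rule is stated, the Month 12 window in Appendix 1 opens on day 1 after treatment, and a planned Month 12 survival table would have no content on that reading.

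It is also fair to say that Part B has no hypotheses, decision rules or efficacy endpoints (Sections 3.1, 3.2 and 5.1), and that Part A has its own report. That limits the consequences. However, Section 1.1 describes Part A follow-up only to 28 days after the infusion, so that report cannot be assumed to hold deaths from then until Part B entry. It is not at hand to check.

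**Conclusion.** The point holds in conditional form. As written, the SAP applies a Part B membership set to survival rates whose clock starts at the end of Part A treatment. If enrolment comes after that date, deaths in between are absent from both numerator and denominator, and by-arm survival is conditional on reaching Part B.

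The overstatement at Month 24 is about q times survival in enrollees: 4.9 points at an assumed q of 5% and survival of 97%, given equal late survival in children not enrolled. It is nil if all subjects are enrolled from the start.

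A reader might infer that survival is probably overstated. The documents do not support that: they give neither death rates nor the time of enrolment, and Step 4 shows that the sign can reverse. Size and sign in this trial are unknown. What is affected is a descriptive by-arm safety estimate, not a test.

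**What to change.** In Sections 4 and 7.2.1, state that:

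- Number of deaths, survival rates at Month 12 and 24, and Kaplan-Meier curves are analysed by Part A arm in all subjects treated in Part A and alive at the date of last day on study treatment.
- Time runs from that date for the rates and the curves alike. The text should say on which side a death on that same day falls.
- All later deaths count, whether or not the child entered Part B. Other subjects are censored at the last date known alive.
- The number treated and the on-treatment deaths are shown by arm beside these results, because the curves are conditional on surviving treatment. The numbers censored before Month 12 and before Month 24 are also given by arm.

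Keep the Part B set for the developmental, hearing, neurological and eye assessments. If the sponsor prefers the Part B set for survival too, use delayed entry and label the result as conditional on Part B entry; delayed entry cannot recover deaths before the first child enters.

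**Cost.** The change is SAP wording plus combining Part A and Part B death and last-contact dates. The SAP does not say which of these dates the Part A database holds, so this needs checking. Reported survival may be less favourable. Children not followed in Part B are censored early, which may be informative. For example, assume q = 5%, 20% of survivors not enrolled, 10% late mortality among them and 97% survival in enrollees. True survival is 0.95 × (0.8 × 0.97 + 0.2 × 0.90) = 90.82%. The SAP as written reports 97.00% (bias 6.18 points); the change gives 0.95 × 0.97 = 92.15% (bias 1.33 points). The bias shrinks but does not vanish. If everyone is enrolled from the start, the only cost is the wording.

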### **5. ENDPOINTS**

#### ***Part B:***

***Long-term Assessments:*** Monitored at 12 and 24 months after completion of study treatment:

- *Developmental progress, audiological and visual acuity assessments;*
- *Safety, assessed by adverse events, and survival.*

#### **5.1. Efficacy Endpoint(s)**

There are no efficacy endpoints evaluated in Part B of the study.

#### **5.2. Safety Endpoints**

Adverse events (AE), including serious adverse events (SAE) and death.

Survival rates at Month 12 and 24 after completion of study treatment.

#### **5.3. Other Endpoints**

##### **5.3.1. Developmental Progress**

1. Measurement from Bayley Scales of Infant Development at Month 12 and Month 24
  - Cognitive;
  - Language;
  - Motor.
2. Measurements from Bayley Scales of Infant Development - Parent at Month 24
  - Social-emotional;
  - Adaptive behavior.

### **5.3.2. Audiological Assessment**

1. Measurements from pure tone audiometry at Month 12 and Month 24:
  - Behavior hearing assessment results;
  - Results by air conduction via phones/headphones; or
  - Results by air conduction via soundfield;
  - Results by bone conduction, when indicated.
2. Measurements from immittance audiometry at Month 12 and Month 24:
  - Results of tympanometry;
  - Results of ipsilateral stapedial reflex.
3. Measurements from otoacoustic emissions assessment at Month 12 and Month 24:
  - Results from transient evoked emission; or
  - Results from distortion product.

### **5.3.3. Neurological Assessment**

Measurements from Hammersmith Infant Neurological Exam at Month 12 and Month 24:

- Cranial nerves score;
- Posture score;
- Movement score;
- Tone score;
- Reflexes and reaction score;
- Neurological exam global score.

### **5.3.4. Ophthalmological Assessment**

Ophthalmological assessment at Month 12 and 24:

- Visual acuity;
- Results from eye examination –anterior segment;
- Results from eye examination – posterior segment.

## **6. HANDLING OF MISSING VALUES**

No imputation is planned for missing data in data analyses.

## **7. STATISTICAL METHODOLOGY AND STATISTICAL ANALYSES**

### **7.1. Statistical Methods**

For continuous variables, summary statistics of n, mean, standard deviation, median, minimum and maximum will be tabulated by treatment group (iNO+ sildenafil vs. iNO alone in Part A of the study).

For categorical variables, n (%) of subjects in each category will be tabulated by treatment group (iNO+ sildenafil vs. iNO alone) in Part A of the study.

For subjects with multiple records in a given visit, the one with assessment date closest to the target visit day (see [Appendix](#)) will be selected for tabulation; for two observations with equal distance from the target visit day, the one assessed at a later time will be selected for tabulation.

All observations will be included in data listings for the endpoints listed below.

### **7.2. Statistical Analyses**

#### **7.2.1. Analysis of Safety Endpoints**

All adverse events will be coded and grouped by system organ class. The incidence of each adverse event will be tabulated by treatment group. Tabulations by maximum severity and treatment group will also be included.

Data listings will be provided for adverse events, serious adverse events and death.

The duration of overall survival will be summarized graphically using Kaplan-Meier plots for each treatment group. Tabular summaries of the Kaplan-Meier curves giving the median, quartiles, mean, standard error of the mean and range of overall survival will also be provided for each treatment group. Number of deaths and survival rate at Month 12 and 24 will be tabulated by treatment group.

#### **7.2.2. Analysis of Development Progress**

For Bayley Scales of Infant Development, summary statistics of composite score and percentile rank will be tabulated by subtest (cognitive, language and motor) and treatment group at Month 12 and Month 24.

For Bayley Scales of Infant Development-Parent, summary statistics of composite score and percentile rank will be tabulated by subtest (social-emotional and adaptive behavior) and treatment group at Month 24.

#### **7.2.3. Analysis of Audiological Assessment**

1. Measurements from pure tone audiometry
  - Behavior hearing assessment results: n (%) of subjects with results of normal, abnormal, incomplete/inconclusive and missing will be tabulated by treatment group at Month 12 and Month 24.

- Results by air conduction via phones/headphones: n (%) of subjects in each category of response (<=20 DB HL, 21-40 DB HL, 41-70 DB HL, 71-90 DB HL, no response, or could not test) will be tabulated by ear (right or left), frequency and treatment group at Month 12 and Month 24.
- Results by air conduction -soundfield: n (%) of subjects in each category of response (<=20 DB HL, 21-40 DB HL, 41-70 DB HL, 71-90 DB HL, no response, or could not test) will be tabulated by frequency and treatment group at Month 12 and Month 24.
- Results by bone conduction: n (%) of subjects with bone conduction, and n (%) of subjects in each type of hearing loss (sensorineural, conductive, mixed, neural or unspecified) will be tabulated by treatment group at Month 12 and Month 24.

## 2. Measurements from immitance audiometry

- Results of tympanometry: summary statistics will be tabulated for peak pressure (sign of + or -) and static acoustic admittance by ear and treatment group at Month 12 and Month 24
- Results of ipsilateral stapedial reflex: n (%) of subjects in each category of assessment (present, absent, undetermined or not assessed) will be tabulated by ear, frequency and treatment group at Month 12 and Month 24.

## Measurements from otoacoustic emissions assessment at Month 12 and Month 24

- For each assessment method (transient evoked emission, distort product etc.), n (%) of subjects in each category of assessment (present, absent, undetermined or not assessed) will be tabulated by ear, frequency and treatment group at Month 12 and Month 24.

### **7.2.4. Analysis of Neurological Assessment**

For scores from each subtest (cranial nerves, posture, movement, tone, and reflexes and reaction), and neurological global exam score, summary statistics will be tabulated by treatment group at Month 12 and Month 24.

### **7.2.5. Analysis of Ophthalmological Assessment**

For visual acuity, the following data analyses will be conducted:

1. n (%) of subjects with amblyopia, strabismus, or nystagmus will be tabulated by eye (right or left) and treatment group at Month 12 and Month 24.
2. For verbal child, n (%) of subjects with visual assessment category of visual acuity chart, counting finger, hand motion, light perception, no light perception will be tabulated by eye and treatment group at Month 12 and Month 24.

3. For verbal child with visual acuity assessed by visual acuity chart, summary statistics of LogMAR visual acuity value will be tabulated by eye and treatment group at Month 12 and Month 24.

LogMAR values will be derived from Snellen scores (or equivalent) by converting to the decimal notation (dividing the numerator of the Snellen fraction by the denominator) and then taking the negative of the logarithm. For example, 20/40 = 0.5 and  $-\log 0.5$  is 0.3.

For eye examinations for anterior and posterior segment, n (%) subjects with results of normal, abnormal and not done will be tabulated by eye (right or left) and treatment group at Month 12 and Month 24.

#### **7.2.6. Other Analyses**

Summary tables with descriptive statistics and data listings will also be provided for medical history, physical examination, and subject disposition (based on CRF of End of Study – Subject Summary).

### **8. APPENDIX**

#### **Appendix 1. DEFINITION AND USE OF VISIT WINDOWS IN REPORTING**

Visit Label	Definition [Day window]
Month 12	Date of Assessment – Date of Last Day on Study Treatment in Part A of the Study: [1 to 540] with target day of 360
Month 24	Date of Assessment – Date of Last Day on Study Treatment in Part A of the Study: $\geq 541$ with target day of 720
